Evaluating patient satisfaction with 2-week post-operative virtual visits compared to in-office visits: A randomized control trial.

Principal Investigators: [name] MD
[name] MD
[name]

[name] DO, [name] MD, [name] MD, [name] MD, [name] MD, [name] MD, [name] CNP, [name] CNP, [name] CNP

Background

Telemedicine is defined as “the use of computer-based technologies to manage a patient’s health by exchanging medical information over a distance”. (Harting, et al). As technologies like smartphones, tablets, and computers have become more integrated into everyday life, they have also been incorporated into medical practice. Telephone visits have been incorporated into a variety of surgical fields, including pediatric surgery, urology, and outpatient general surgery (Young, et al; Finklestein, et al; Soegaard Ballester, et al) and are associated with decreased overall visit times and shortened or eliminated travel times (Soegaard Ballester, et al.).

Virtual visits (visits conducted face-to-face using computers, tablets, or smartphones) have grown in popularity. A systematic review noted that the concerns of physicians conducting telephone-based care included potential risk of missing a serious condition, inability to use visual cues, and inability to conduct a physical exam. (Car, et al.) Virtual visits add back a visual component of an in-person visit, while preserving the above benefits of telephone visits. In the General Surgery literature, patients attending virtual visits after outpatient surgery reported higher levels of satisfaction than their in-person counterparts. (Healy, et al.)

Telemedicine has been introduced in obstetrics for prenatal care, monitoring of chronic conditions during pregnancy, genetic counseling, medical abortion, and colposcopy (Kohn, et al., Griener). A randomized control trial in urogynecology in 2019 demonstrated that telephone-based postoperative visits were non-inferior to in-person postoperative visits in terms of patient satisfaction. (Thompson, et al.) Although utilization of telemedicine in OB/GYN is expanding, there is still a dearth of literature, particularly regarding virtual visits in gynecology. The Cleveland Clinic has instituted telemedicine with the provision of virtual visits in all specialties. In benign gynecologic surgery, virtual visits have been offered in the last couple of years as an alternative to the in-person 2-week post-operative visit, but have not been evaluated systematically.

Our study aims to evaluate the safety and efficacy of virtual postoperative visits as compared to in-office postoperative visits for patients undergoing minimally invasive hysterectomy. We hypothesize that virtual visits will be non-inferior to in-person visits in terms of patient satisfaction. The primary objective for this study is to evaluate patient satisfaction of their postoperative visit experience, as measured by the Press Ganey Medical Practice Survey and Medical Practice Telemedicine Survey (Presson, et al). The secondary objectives include evaluating the incidence of a new diagnosis of a postoperative complication requiring medical treatment (e.g. calling in of a prescription), an office visit with CNP or MIGS surgeon, or an urgent care or ER visit. Post-operative complications include infection (urinary, pulmonary, wound, pelvic abscess, bloodstream), thromboembolic events, bleeding; and issues with wound healing, such as dehiscence. We will record no-show rates, visit times, and estimated travel distance as measured by distance of home to clinic site (Srikrishna, et al).

Study Methods:

This is a two arm, randomized non-inferiority clinical trial.

Setting

This study will take place within the Minimally Invasive Gynecologic Surgery division in the Women's Health Institute of the Cleveland Clinic, Cleveland, OH.

Population

We will recruit patients undergoing benign minimally invasive hysterectomy (laparoscopic, robotic, and vaginal). Inclusion criteria include patients >18 years of age who are able to provide informed consent without assistance, speak English, and who have access to a phone or device equipped for virtual visits. Patients will be excluded if the staff surgeon determines they are inappropriate for virtual follow-up, if there is suspicion of malignancy, if they are unable to provide consent, or if they do not have access to technology that enables virtual visits.

Inclusion criteria	Exclusion criteria
>18 years of age	Deemed ineligible by staff surgeon
Able to provide consent without assistance	Suspicion of malignancy
English-speaking	Unable to provide consent
Access to phone or device equipped for virtual visits	Do not have access to technology for virtual visits

Recruitment

Enrolled participants will be randomized to either a two-week virtual postoperative visit with a certified nurse practitioner (CNP) or a two-week in-office postoperative visit with a certified nurse practitioner (CNP) in a 1:1 allocation ratio. Block randomizations with block size of 4 will be assigned to nurse providers independently. Randomization schedules will be implemented by Redcap.

Data collection

The primary outcome of this study is patient satisfaction, as measured by the Press Ganey Medical Practice Survey and Medical Practice Telemedicine Survey. These questionnaires will be sent via RedCap on the day of their two-week postoperative appointment. We will provide verbal reminders about study participation and survey administration at the visit. If participants have not responded by their six-week visit, a scripted phone call will be made as a reminder. The secondary outcome is a new diagnosis of a postoperative complication requiring medical treatment (e.g. calling in of a prescription), an office visit with a CNP or MIGS surgeon, or an urgent care or ER visit. Complications include infection (urinary, pulmonary, wound, pelvic abscess, bloodstream); thromboembolic events; bleeding; and issues with wound healing, such as dehiscence. Calvien-Dindo classification system for postoperative complications will be used. We will also look at no-show rates, visit times, and travel distance.

We will collect basic demographic information from the EMR, including MRN, age, email address, BMI, race, insurance status, parity, and prior surgical history. Date of enrollment, date of surgery, date of admission, and date of discharge will be recorded. Surgical indication, procedure performed, length of hospital stay, and perioperative outcomes (reoperation, readmission, unscheduled office or virtual visits (i.e. earlier than the scheduled 2 week visit), ED/urgent care visits, infection rates) will also be obtained. No-show rates will be obtained through the EMR. We will also note if a planned virtual visit is unable to be completed due to

technical difficulties, or is converted to a telephone visit. We will collect date of their 6 week postoperative visit or date they withdrew from the study. We will collect zip code; travel distance from home to clinic site will be calculated using average travel time with minimal traffic based on participant's zip code using Google Maps.

We will collect the reason for ineligibility for all patients deemed such by staff surgeons.

All participants will be assigned a study number to facilitate de-identification of data.

Data will be compiled in RedCap and securely stored on an encrypted server.

Statistical analysis

Power Calculation:

We hypothesized that patient satisfaction would be non-inferior for patients randomized to the postoperative virtual visit compared to those randomized to in-person virtual visit (Thompson, et al). Sample size of 70 patients in each arm is needed to achieve 90% power to detect a non-inferiority margin of -0.20. Allowing for a dropout rate of 20%, 88 patients will be recruited in each arm.

Analysis plan:

For the primary outcome, the Farrington-Manning score test for non-inferiority will be performed, for both intention-to-treat and per-protocol analyses. Approximately normally-distributed continuous measures will be summarized using means and standard deviations and will be compared using two-sample t-tests. Continuous measures that show departure from normality and ordinal measures will be summarized using medians and quartiles and will be compared using Wilcoxon rank sum tests. Categorical factors will be summarized using frequencies and percentages and will be compared using Pearson's chi-square tests or Fisher's Exact tests.

All analyses will be done using SAS (version 9.4, The SAS Institute, Cary, NC) and a $p < 0.05$ will be considered statistically significant.

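### Safety is a stated aim, but complications are compared only by a test of difference with no interval, so a non-significant result would leave a sizeable excess unexcluded

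*Combined protocol and SAP*

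**What the plan says.** The Background sets a comparative safety aim: "Our study aims to evaluate the safety and efficacy of virtual postoperative visits as compared to in-office postoperative visits". The hypothesis that follows covers only one part of it: "We hypothesize that virtual visits will be non-inferior to in-person visits in terms of patient satisfaction". Complications are the secondary outcome (Background and Data collection). They are defined as newly diagnosed complications that lead to medical treatment, an office visit, or urgent or emergency care, and they are to be graded by Clavien-Dindo.

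Under Statistical analysis, the sample size is set for satisfaction: "Sample size of 70 patients in each arm is needed to achieve 90% power to detect a non-inferiority margin of -0.20", then "Allowing for a dropout rate of 20%, 88 patients will be recruited in each arm". The non-inferiority test is limited in the same way: "For the primary outcome, the Farrington-Manning score test for non-inferiority will be performed, for both intention-to-treat and per-protocol analyses". The occurrence of complications falls under the general rule: "Categorical factors will be summarized using frequencies and percentages and will be compared using Pearson's chi-square tests or Fisher's Exact tests", with the threshold "a $p < 0.05$ will be considered statistically significant". The plan gives no expected complication rate, margin or confidence interval for complications, and it does not say how a non-significant comparison will be interpreted.

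**The concern.** For safety, the question is whether replacing the in-office visit makes outcomes worse. The protocol recognises this logic for satisfaction and uses a non-inferiority design there. For complications it uses a test whose null hypothesis is no difference. When such a test is not significant, it says only that a difference was not shown. It does not say how large a difference remains possible.

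Because safety is a named aim and the p-value is the only planned comparative result, a report of non-inferior satisfaction with no significant difference in complications could be taken as meeting both halves of the aim. The Background cites clinicians' worry, in telephone care, about overlooking a serious condition. It also says the service is already offered but has not been systematically evaluated. An unsupported safety conclusion would therefore have practical consequences.

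**Working it through.** **Inputs.** From the Power Calculation: 70 per arm needed, 20% dropout, 88 per arm recruited. From the Analysis plan: chi-square or Fisher, 0.05 (sidedness is not stated; two-sided is used here). Assumptions: each patient counts once, as having a complication or not; in-office rates are 5, 10, 15 or 20%, because the documents give none.

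**1. The plan's own figure.** 70 / (1 - 0.20) = 87.5, rounded up to 88 per arm. This reproduces. The figure of 70 concerns satisfaction and is not in dispute here. It serves below as the number left per arm if the full planned dropout occurs.

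**2. How often a true doubling is missed.** The chi-square test without correction is equivalent to

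z = (p1 - p2) / sqrt[ p̄(1 - p̄) × 2/n ], significant if |z| > 1.96,

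where p̄ is the pooled proportion. Summing the binomial probabilities of all non-significant tables gives the chance of missing the doubling:

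| In-office v virtual rate (assumed) | 88 per arm | 70 per arm |
|---|---|---|
| 5% v 10% | 77% | 80% |
| 10% v 20% | 54% | 62% |
| 15% v 30% | 32% | 42% |
| 20% v 40% | 16% | 25% |

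Fisher's test misses more: with 88 per arm its power is 17, 39, 60 and 79%, so it misses about 83, 61, 40 and 21%.

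**3. An observed doubling, 12/88 virtual v 6/88 in-office.** The proportions are 0.1364 and 0.0682, a difference of 0.0682. The pooled proportion is 18/176 = 0.1023. The standard error is sqrt(0.1023 × 0.8977 × 2/88) = 0.0457, so z = 1.49 and chi-square p = 0.14. Fisher gives p = 0.21.

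Newcombe's interval uses the Wilson limits of each proportion: 0.0798 to 0.2234 (virtual) and 0.0316 to 0.1409 (in-office).

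- Lower: 0.0682 - sqrt[(0.1364 - 0.0798)² + (0.1409 - 0.0682)²] = 0.0682 - 0.0921 = -0.024
- Upper: 0.0682 + sqrt[(0.2234 - 0.1364)² + (0.0682 - 0.0316)²] = 0.0682 + 0.0944 = +0.163

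The interval is -2.4 to +16.3 percentage points.

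**4. Identical counts, 9/88 v 9/88.** Each proportion is 0.1023, with Wilson limits 0.0547 to 0.1831. The half-width is sqrt[(0.1831 - 0.1023)² + (0.1023 - 0.0547)²] = 0.094. Even with no observed difference, an excess of up to 9.4 points remains possible. At 4 v 4, 13 v 13 and 18 v 18 the corresponding limits are 7.1, 10.7 and 11.9 points.

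**5. A larger observed excess, 18/88 v 9/88.** Chi-square gives p = 0.06, still not significant. The interval is -0.5 to +20.9 points.

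**The case against.** The case for leaving the plan alone has several parts.

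- **Safety is secondary.** The title, the hypothesis and the primary objective all concern satisfaction, and the secondary objective speaks of evaluating incidence. Limited power for a secondary outcome is normal. This stands: the sample size is not at fault. But the aim still names safety, and the outcome is never declared descriptive.
- **No false rule is written down.** A reader might infer that the plan will declare virtual visits safe if p exceeds 0.05. The documents do not say so. The supported statement is that nothing in the plan prevents that reading.
- **A doubling may well be detected.** A reader might infer that the test would usually miss a doubling whatever the rate. That holds only at assumed rates of about 10% or below. At 20% a doubling is found 84% of the time with 88 per arm. The outcome is broad, so a low rate cannot be presumed.
- **Counts and percentages are planned.** A reader could derive the interval from them. This also stands: what is missing is a pre-specified interval on which the trial's own conclusion rests.
- **Follow-up.** A reader might take six weeks as the window for complications. The protocol records the date of the six-week visit or of withdrawal, but states no counting window. The calculations do not depend on one.
- **Clavien-Dindo grades** might be compared as an ordinal measure by the Wilcoxon test. That too is a test of difference without an interval, so the gap remains.

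**Conclusion.** The point holds as a gap between aim and analysis. The planned comparison cannot show that virtual visits are no worse for complications, and the plan specifies no interval to show what excess remains possible. It is not an error in the primary analysis or the sample size, and it does not establish that the authors will claim safety from a non-significant test.

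The size depends on assumed rates. Over 5 to 20% in-office, a true doubling is missed about 77 to 16% of the time with 88 per arm, or 80 to 25% with 70, by chi-square. The need for an interval does not depend on the rate: equal counts leave an excess of about 7 to 12 points unexcluded across that range.

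A reader might also infer that the upper confidence limit alone would settle safety. It would not. The outcome is a new diagnosis, and a condition missed at a virtual visit would lower the recorded rate in that arm. An apparent benefit therefore needs as much care as an apparent harm.

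**What to change.** 1. In the Analysis plan, make the virtual-minus-in-office risk difference in the secondary complication outcome, with its 95% confidence interval (for example Newcombe), the safety result. The chi-square or Fisher p-value may be kept beside it.
2. State there that p>0.05 will not be taken as evidence of equal safety.
3. In the Background, word the safety aim as estimating this difference, and say that the whole interval will be interpreted because missed diagnoses could lower the recorded rate in the virtual arm.

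The cost is a few sentences and one extra option in the SAS analysis. No data, visits or patients are added, and the primary analysis is unchanged. The downside is a less favourable safety statement: with arms of this size the interval will probably be wide, and the report will have to say so.

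### Randomisation is blocked separately by nurse, but the primary Farrington-Manning test ignores nurse: slightly conservative if nurses differ, biased if losses also differ by nurse and arm

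*Combined protocol and SAP*

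**What the plan says.** Under Recruitment, participants are allocated 1:1 to a virtual or an in-office two-week visit with a nurse practitioner, and "Block randomizations with block size of 4 will be assigned to nurse providers independently". The natural reading is one independent schedule of blocks of four for each nurse.

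Under Statistical analysis, the Analysis plan states: "For the primary outcome, the Farrington-Manning score test for non-inferiority will be performed, for both intention-to-treat and per-protocol analyses". It mentions no stratum, covariate or sensitivity analysis by nurse. The Power Calculation does not mention nurse either: "Sample size of 70 patients in each arm is needed to achieve 90% power to detect a non-inferiority margin of -0.20", and then "Allowing for a dropout rate of 20%, 88 patients will be recruited in each arm".

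Two statements under Data collection bear on who ends up in the analysis. On the survey: "We will provide verbal reminders about study participation and survey administration at the visit". On the virtual arm: "We will also note if a planned virtual visit is unable to be completed due to" technical problems, or is switched to telephone. Nurse is not among the data items listed there.

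**The concern.** The outcome is satisfaction with a visit that the nurse conducts, so differences between nurses are plausible. A test that ignores a randomisation stratum related to the outcome uses a standard error that includes between-nurse variation already removed by the blocking. That error is on the safe side.

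The second consequence is not always safe. Blocking guarantees nurse balance only among those randomised. Survey return may depend on what happens at the visit, which differs by nurse and by arm, and failed virtual visits can occur in one arm only. If the analysed arms end up with different nurse mixes, a pooled difference confounds visit type with nurse. In a non-inferiority trial, a shift towards zero raises the chance of a false claim, and a shift the other way costs power. Running both intention-to-treat and per-protocol analyses gives no protection, because both would be pooled.

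**Working it through.** **The plan's own figures.** 70 / (1 − 0.20) = 87.5, rounded up to 88, so the recruitment figure reproduces. The 70 cannot be checked, because neither a satisfaction rate nor the sidedness of the test is given.

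**Inputs from the documents.** 88 randomised per arm; about 70 analysed; margin −0.20; separate blocks per nurse; 1:1 allocation.

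**Assumptions.** Three nurses (three nurse practitioners appear in the investigator list; the number running visits is not stated), with 30/29/29 patients per arm. A binary endpoint with office satisfaction averaging 80%. Nurse rates of 80/80/80, 70/80/90 or 65/80/95%. One-sided 2.5% (the plan says only p < 0.05). All response patterns are assumed.

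**Tests compared** (V virtual, O office; p̃ is the estimate restricted to a difference of −0.20)
- Pooled: z = (p̂_V − p̂_O + 0.20) / √[p̃_V(1−p̃_V)/n_V + p̃_O(1−p̃_O)/n_O].
- Stratified: d = Σw_k d_k / Σw_k, with w_k = n_Vk n_Ok/(n_Vk + n_Ok). Its variance is Σw_k² v_k /(Σw_k)², where v_k is the restricted variance in nurse k times N_k/(N_k − 1).

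**Step 1: standard error.** Take office 70/80/90% and virtual 50/60/70%.
- Pooled variance terms: 0.8×0.2 + 0.6×0.4 = 0.400.
- Within-nurse averages: (0.21+0.16+0.09)/3 + (0.25+0.24+0.21)/3 = 0.387.
- With complete data the pooled standard error is too large by √(0.400/0.387) − 1 ≈ 1.7%.

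Random non-response undoes part of the blocking, and the variance estimate runs slightly low at about 70 per arm. The simulated excess is therefore smaller: 0.9% here and 2.7% at 65/80/95%.

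**Step 2: bias.** With equal caseloads, the expected pooled proportion in an arm is Σr_k p_k / Σr_k, where r_k is the response rate. The true difference is −0.20 within every nurse, and office rates are 70/80/90%.
- Response 70/80/90% in both arms: V = (0.35+0.48+0.63)/2.4 = 0.608; O = (0.49+0.64+0.81)/2.4 = 0.808. Difference −0.200, no bias.
- V 70/80/90%, O 80% throughout: 0.608 − 0.800 = −0.192, bias +0.8 points.
- V 70/80/90%, O 90/80/70%: O = (0.63+0.64+0.63)/2.4 = 0.792. Difference −0.183, bias +1.7 points.

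**Step 3: simulation.** 200,000 trials per scenario; Monte Carlo error is about 0.04 points on type I error and 0.1 on power. Ranges cover nurse rates 70/80/90% and 65/80/95%.

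| Loss pattern | Pooled bias (points) | Type I error, pooled | Type I error, stratified |
|---|---|---|---|
| 80% response everywhere | 0 | 2.2–2.4% | 2.5–2.6% |
| V 70/80/90, O 80 | +0.8 to +1.3 | 3.1–3.4% | 2.5–2.6% |
| V 70/80/90, O 90/80/70 | +1.7 to +2.6 | 4.1–4.9% | 2.5–2.6% |
| Per-protocol: V loses a further 20/10/0% | +0.8 to +1.1 | 3.0–3.2% | 2.5% |

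- If nurses do not differ, type I error with equal response is 2.6% pooled and 2.5% stratified.
- With the crossed pattern reversed, bias is −1.7 to −2.5 points and pooled power is 77.3% to 73.5%, against 83.6% to 84.4% stratified.
- At one-sided 5%, the crossed pattern gives 7.7–8.9% pooled and 5.0–5.1% stratified.
- With unequal caseloads (44/28/16 or 16/28/44 per arm), the crossed pattern gives 3.8–4.6% pooled and 2.5–2.6% stratified.
- With equal response, power is 83.8% pooled and 83.4% stratified (nurses alike), 84.0% and 84.1% (70/80/90), and 84.6% and 85.1% (65/80/95).

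A separate run with satisfaction averaging 84% and losses crossed in the direction that favours virtual visits gave pooled type I error of 3.7% (nurse rates 92/84/76%) and 4.8% (98/84/70%).

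**The case against.** The only effect that follows from the design and the test alone is small and conservative. The bias needs three things together: nurses differ in satisfaction, losses differ by nurse, and the nurse pattern of loss differs by arm. The documents supply no rates for any of these, and the crossed pattern is a stress case. A milder crossing (response 75/80/85% against 85/80/75%, nurse satisfaction 75/80/85%) gives +0.4 points of bias and 2.9% against 2.5%. If only the virtual arm varies, it gives +0.2 points and 2.7%. Those shifts are small beside a 20-point margin and a standard error of about 7.5 points.

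Surveys also go out through REDCap, and non-responders get a scripted call by six weeks, whichever nurse they saw. The plan does not say that the nurse gives the verbal reminder. It never says that failed virtual visits leave the per-protocol set, which is undefined. The 80% base case gives about 84% power at one-sided 2.5%, not the stated 90%. Finally, the bias is partly a missing-data problem that stratifying cannot fully solve.

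All of this stands as a limit on the likely size. None of it supplies a reason to leave nurse out of the analysis: the plan still budgets for 20% loss, states no rule for missing surveys, and names a test that does not match its randomisation.

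**Conclusion.** The concern holds and is minor. With losses alike in the two arms, pooling costs at most about 0.3 points of type I error, on the conservative side, and changes power by no more than 0.5 points. With losses that differ by nurse and arm, it can claim non-inferiority too often (roughly 3–5% instead of 2.5% in the patterns tested) or too rarely. The stratified test keeps its level and an unbiased estimate in every pattern.

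The sizes rest on assumed nurse numbers, satisfaction rates, loss patterns, a binary endpoint and a one-sided 2.5% level. That the analysis will be pooled is inferred from the plan naming no stratum. If a stratified test is intended, the plan needs to say so. Stratifying removes only the part of the bias explained by nurse, not non-response that depends on satisfaction within a nurse.

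**What to change.** Replace the primary-outcome sentence of the Analysis plan with wording such as: *a Farrington-Manning/Miettinen-Nurminen score test stratified by the nurse schedule used for randomisation, with Mantel-Haenszel weights and restricted-maximum-likelihood variance per stratum including the n/(n − 1) factor; the stratified difference and its confidence interval are compared with −0.20 in both the intention-to-treat and per-protocol sets.*

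State in advance how a nurse with no analysed patients in one arm is merged with another. Keep the pooled test as a sensitivity analysis, and tabulate survey response and per-protocol exclusions by nurse and arm.

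The cost is one sentence and one small table. Nurse is not a listed data item, but it should be recoverable from the per-nurse REDCap schedules. If nurses do not differ, stratifying loses 0.3–0.8 points of power. Making the change before outcomes are seen also rules out choosing between pooled and stratified results afterwards.

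### Survey non-responders are first chased by phone about four weeks after the visit they rate, and no analysis tests whether non-inferiority depends on the missing answers

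*Combined protocol and SAP*

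**What the plan says.** The objectives at the end of the introductory text make it the primary aim to "evaluate patient satisfaction of their postoperative visit experience", using Press Ganey surveys that patients complete themselves.

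Data collection describes three contacts about the survey:

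- Sending: "These questionnaires will be sent via RedCap on the day of their two-week postoperative appointment".
- At the visit: "We will provide verbal reminders about study participation and survey administration at the visit".
- Afterwards: "If participants have not responded by their six-week visit, a scripted phone call will be made as a reminder".

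The same section expects some visits not to go as planned. It says "No-show rates will be obtained through the EMR", and it records virtual visits that fail for technical reasons or become telephone visits.

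Under Power Calculation: "Sample size of 70 patients in each arm is needed to achieve 90% power to detect a non-inferiority margin of -0.20", and then "Allowing for a dropout rate of 20%, 88 patients will be recruited in each arm". The Analysis plan names the Farrington-Manning test for the intention-to-treat and per-protocol sets. It does not say how a randomised patient without a survey enters either set, and it contains no sensitivity analysis for missing answers.

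**The concern.** The spoken reminder is given before anyone can know who will fail to answer, and it reaches only people who attend. After it, nothing aimed at non-responders is written down until about week six. An answer obtained then is a late recollection of the two-week visit and may also reflect the six-week visit. As written, no-shows in either arm get no earlier prompt. A virtual visit that fails technically may get none, because the text does not say what contact takes place.

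The outcome is the patient's own rating, and the plan names no other source for it. Non-response unrelated to satisfaction costs only power. Selective non-response can bias the comparison in either direction: towards non-inferiority if dissatisfied virtual-arm patients are lost more often, against it if dissatisfied in-office patients are. Technical failure of the visit is one possible route to non-response that exists only in the virtual arm. Running both analysis sets does not help, because they differ on adherence and both need an observed answer.

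**Working it through.** **Timing.** Week 6 minus week 2 is about four weeks. This is nominal, because no exact call date is given.

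**The plan's own figure.** 70 / (1 − 0.20) = 87.5, rounded up to 88 per arm, 176 in all. This reproduces. It leaves room for 88 − 70 = 18 patients per arm without a survey, if the whole allowance is used that way.

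**Assumptions.** The documents give no satisfied/not-satisfied cut-off, no in-office satisfaction rate, no expected survey non-response and no sidedness for the non-inferiority test. I assume a binary outcome. Exact Farrington-Manning power with 70 per arm and margin −0.20 is 0.906 at 80% versus 80% (one-sided 5%) and 0.898 at 85% versus 85% (one-sided 2.5%). Either pair fits the stated 90%. The main illustration uses 80% and one-sided 5%.

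**False non-inferiority with the truth at the margin.** True rates are 60% virtual and 80% in-office. With 70 per arm and no selective loss, the exact rejection probability is 0.053.

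*Selective loss in the virtual arm only.* If a fraction L is lost and a fraction q of those lost are satisfied, the responder rate is (0.60 − L × q) / (1 − L). For L = 0.20 and q = 0.40 this is (0.60 − 0.08) / 0.80 = 0.65. These rows hold the in-office arm at 70 responders, an unbiased 80% sample.

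| Virtual loss (responders) | Responder rate, q = 0.40 / 0.20 | False non-inferiority, one-sided 5% | One-sided 2.5% |
|---|---|---|---|
| 5% (84) | 0.611 / 0.621 | 0.071 / 0.094 | 0.034 / 0.047 |
| 10% (79) | 0.622 / 0.644 | 0.089 / 0.151 | 0.046 / 0.087 |
| 20% (70) | 0.65 / 0.70 | 0.171 / 0.401 | 0.101 / 0.283 |

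*Same responder-minus-non-responder gap g in both arms.* The responder rate is the true rate plus L × g. For L = 0.20 virtual, 0.10 in-office and g = 0.25, the rates are 0.65 and 0.825.

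| Loss, virtual vs in-office | g = 0.25 | g = 0.50 |
|---|---|---|
| 20% vs 20% | 0.052 | 0.051 |
| 10% vs 5% | 0.074 | 0.104 |
| 20% vs 10% | 0.100 | 0.181 |

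*Selective loss in the in-office arm only.* With 20% lost and 60% or 40% of them satisfied, the in-office responder rate is 0.85 or 0.90. False non-inferiority falls to 0.010 or 0.001.

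*Alternative truth,* 65% versus 85% at one-sided 2.5%, virtual-only loss, 45% or 25% of non-responders satisfied: 0.035 / 0.050 at 5% loss, 0.055 / 0.104 at 10% and 0.107 / 0.313 at 20%. The pattern is the same.

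**Tipping points.** Put the non-responders back, so that 88 per arm are analysed at one-sided 5%.

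- 56/70 satisfied in each arm, 18 missing per arm, 14 of 18 in-office non-responders satisfied: non-inferiority is lost at 5 or fewer of 18 virtual. It is never lost if 7 or fewer in-office non-responders are satisfied.
- 52/70 versus 56/70, where the responders-only z is 2.01 and the test succeeds: lost at 9 or fewer of 18 virtual, again with 14 of 18 in-office.
- 63/79 in each arm, 9 missing per arm: lost only if 0 of 9 virtual and 9 of 9 in-office non-responders are satisfied.

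**The case against.** The strongest reply is that the call's timing is a design choice that contradicts nothing. All three contacts apply to both arms, the survey can be answered from the first day, and the delay touches only patients still silent. The calculations model selective loss, not late recall, and none shows how far an earlier call would cut the loss. The call might also come before the six-week visit. All of this is fair. The benefit of earlier contact is plausible but not quantified, and influence from the six-week visit is only a possibility.

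The large error rates also need several assumptions at once: truth exactly at the margin, substantial loss, and loss that is both selective and unequal. With equal loss and an equal gap the error stays at 5%, and the 56/70 example survives all but a marked imbalance among non-responders. That also stands, and it limits the weight of the point. It does not remove the gap, because a closer result such as 52/70 versus 56/70 is sensitive and the plan gives readers no means of seeing which situation applies.

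Two further objections are that a no-show has no visit to rate, and that a tipping-point analysis needs a satisfied/not-satisfied cut-off. The first calls for its own handling rule, which is part of the fix. The second is needed for the planned primary test in any case.

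**Conclusion.** The concern holds. Targeted follow-up of survey non-responders starts nominally four weeks after the visit being rated, and the plan has no analysis of whether its primary conclusion depends on missing answers. The dropout allowance preserves numbers, not comparability.

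The possible size runs from nothing (equal loss, equal gap) through 7–18% false non-inferiority when loss is unequal (10% versus 5%, or 20% versus 10%) with the same gap in both arms, to 17–40% in the worst case of 20% selective loss confined to the virtual arm, against a nominal 5%. Selective in-office loss moves the error the other way, to 1.0–0.1%. All these rest on assumed satisfaction and non-response rates, and the documents do not show that response will be poor or unequal. This is an improvement the plan should make, not a defect that invalidates the design. Confidence is medium.

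**What to change.** **Data collection.** Send automated RedCap reminders and make the existing scripted call to every randomised patient who has not answered, shortly after the scheduled two-week date, for example within about a week. Do this identically in both arms, and include no-shows and failed or converted visits. Keep the six-week call as a last attempt, and record the date of each response.

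**Analysis plan.** Report survey response by arm. Add one two-way tipping-point analysis of the Farrington-Manning conclusion that varies satisfaction among non-responders in both arms. State separately how patients with no visit to rate are handled. Do not rely on counting missing answers as dissatisfied.

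**Cost.** Low. Email addresses, no-shows, failed or converted virtual visits and the six-week date are already collected. If 20–40% have not answered after a week (assumed), that is 0.20 × 176 ≈ 35 to 0.40 × 176 ≈ 70 calls. Over the planned 7–8 months this is between 35 / 8 ≈ 4 and 70 / 7 = 10 a month, made by existing staff, plus one further table in the analysis.
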